#### **5.6. Patient Withdrawal Criteria**

Patient participation in the study is purely voluntary; patients can withdraw consent at any time for any reason without effect on subsequent care. This is an open-label study in which the investigator is aware of the patient's treatment assignment. The investigator, in consultation with the Medical Monitor, or the Medical Monitor may exercise his or her medical judgment to terminate a patient's participation in the study due to clinically significant changes in any clinical or laboratory parameter. If in the opinion of the investigator, the patient is failing the study drug for lack of efficacy, as evidenced by an excessive decline of FVC, during Part A of the study, the patient can be withdrawn and placed on alternative therapies. During Part B of the study, the investigator may choose to add nintedanib, but not oral pirfenidone, to the patient's treatment regimen.

Any randomized patient desiring to discontinue prior to study completion should be encouraged to discuss his or her reasons and concerns with the investigator. If, after discussion, the patient still chooses to discontinue participation in the study, the patient should be encouraged to attend an Early Termination visit. (Patients that discontinue during the screening process will be considered screen failures.) Patients who are discontinued during a scheduled visit will be encouraged to complete all unique assessments for both that study visit and the End of Treatment visit at the time of discontinuation. If a patient is still participating in Part A and has had a HRCT scan within the past month, the HRCT from the End of Treatment visit will not be performed.

An End of Study case report form (CRF) page will be completed for every patient who receives study medication whether or not the patient completes the study. The reason for any early discontinuation from the study will be indicated on this form. The primary reason for any early termination will be selected from the following standard categories:

- Adverse Event: Clinical or laboratory events occurred that in the medical judgment of the investigator, in consultation with the Medical Monitor and Avalyn Pharma, represents an unacceptable risk to the patient if he/she continues in the study. This includes serious and non-serious AEs regardless of relationship to study medication. The investigator must follow the patient until the AE resolves or satisfactorily stabilizes

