#### **6.2.11 Follow-up Visit for Patients NOT Enrolling in AP01-005 (28 days +/- 7 days after the Visit 12 - End of Study visit)**

Follow-up visits will occur 28 days after the End of Study visit for Part B. The following procedures will be conducted in chronological order:

- Cough VAS, KBILD Questionnaire and LCQ
- AEs and concomitant medications since previous visit
- Modified PE (Lungs and CV body systems only)
- Vital signs
- SaO2
- Spirometry and DLCO
- Blood samples for laboratory tests (Chemistry including AST and ALT, Hematology, Biomarkers (CA19-9 and CA-125 only))
- Urinalysis
- End of Study form completion

Patients may experience AEs that necessitate an unscheduled visit. There may also be situations in which the investigator asks a patient to report for an unscheduled visit following the report of an AE or a significant decrease in FVC during home spirometry readings. Additional examinations may be conducted at these visits as necessary to ensure the safety and well-being of patients during the study. Electronic case report forms (eCRFs) should be completed for each unscheduled visit.

Avalyn Pharma, Inc.  
AP01-002

Protocol V2.1  

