8.1. Primary Efficacy Endpoint and Analysis

Spirometry will be conducted at approximately the same time each visit (within 60 minutes of Day 1 spirometry measurement) with the patient in seated position. The test will be performed to American Thoracic Society/European Respiratory Society (ATS/ERS) guidelines³. On days of clinic visits (including the screening visit), patients must refrain from strenuous activity at least 12 hours prior to pulmonary function testing (PFT). FVC % predicted will be calculated using the ERS Global Lung Function Initiative 2012 equations² as outlined in the clinical study manual.

PFTs will be collected at Screening, Baseline and at each post-Baseline time point (Week 4, 8, 12, 16, 20, 24, 36, 48, 60, 72 and Follow-Up) as described in Section 6.1.

The primary efficacy endpoint is the change from baseline in absolute FVC % predicted from Baseline to Week 24. The population used for efficacy analyses of the primary variable will be the PP with the FAS used for the first sensitivity analyses.

A linear mixed-effects model (PROC MIXED) will be used and differences between treatment groups between slopes estimating the change from baseline in absolute FVC % predicted from Baseline to Week 24 will be examined. Baseline FVC % predicted, region, age at screening, sex, baseline DL_{CO} % predicted, and baseline progression-related biomarker (CXCL13, CCL18, MMP3) values each categorized as >Median level vs. ≤Median level will be included as covariates in the model. This analysis requires at least three post-baseline FVC % predicted values in addition to baseline be available for a patient to be included in the analysis so that the slope estimated is identifiable. Similar modeling strategies will be employed for longer-term data obtained from Part B of the study. Spirometry data collected after patients switched dosing regimen from 50 mg once daily to 100 mg twice daily will be omitted for this analysis.

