The following statistics for in-clinic FVC and FVC % Predicted will be calculated and summarized by treatment group and displayed in a table:

- Summary statistics of in-clinic FVC and FVC % Predicted at Baseline and at each post-Baseline time point (Week 4, 8, 12, 16, 20, 24, 36, 48, 60, 72 and Follow-Up)
- Summary statistics of in-clinic FVC and FVC % Predicted reflecting the absolute change from Baseline to each post-Baseline time point (Week 4, 8, 12, 16, 20, 24, 36, 48, 60, 72 and Follow-Up).

The following plot will be produced for in-clinic FVC and FVC % Predicted:

- Mean FVC (or FVC % Predicted) Change from Baseline (\pm SD) vs. Visit Week (Week 4, Week 8, Week 12, etc.) with lines for each treatment group.

Linear mixed-effects models (PROC MIXED) will be used for the analyses. The model will include the change from baseline in in-clinic FVC (or FVC % Predicted) (measured at any time in the study) as the dependent variable and will include patient and time (continuous) as random effects, fixed effect of time and time-varying effects for treatment group and treatment-by-time interaction to account for those patients who switched dosing regimens from 50 mg once daily to 100 mg twice daily in Part B. Longitudinal plots at selected timepoints displaying the model adjusted, least square means and 95% confidence intervals will be produced.

All in-clinic pulmonary function data will be presented in a listing.

8.2. Secondary Efficacy Endpoint(s) and Analyses**8.2.1. Change from baseline in cough frequency as measured by LCM**

The LCM⁴ is an audio-based cough detection device that allows sounds to be reconstructed and measured as cough events. Patients that pass all of the screening criteria and will be randomized in the study will be provided with a cough monitor to wear for a 24-hour period prior to coming in for their Baseline visit. This will be used as their baseline reading. The LCM and mailing materials will also be dispensed at Visits 5 and 8. Patients will wear for a 24-hour period, fill out the cough monitor paper diary

This document is confidential.

SAP Version: 3.0 (15JUL2021)
Controlled Document ID: **3903A.01**, Effective Date 29-Oct-2018
Filing requirements: TMF

Page 32 of 52

Statistical Analysis PlanSponsor: Avalyn Pharma, Inc.; Protocol No.: AP01-002

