8.2.6. Change from baseline in D_{LCO}

D_{LCO} will be collected at each visit. For predicted normal values, different sites may use different prediction formulas, based on the method used to measure D_{LCO} . In any case, the method used must be in compliance with the ATS/ERS guidelines⁵ on D_{LCO} measurements and the prediction formula appropriate for that method⁷. Raw data (gas mixture, equation used for prediction of normal, further adjustments made if so) must be traced.

PFTs will be collected at Screening, Baseline (pre-dose and post-dose) and at each Post-Baseline time point (Week 4, 8, 12, 16, 20, 24, 36, 48, 60, 72 and Follow-Up) as described in Section 6.1.

The following statistics for D_{LCO} and D_{LCO} % Predicted will be calculated and summarized by treatment group and displayed in a table:

- Summary statistics of D_{LCO} and D_{LCO} % Predicted at Baseline and at each post-Baseline time point (Week 4, 8, 12, 16, 20, 24, 36, 48, 60, 72 and Follow-Up)
- Summary statistics of D_{LCO} and D_{LCO} % Predicted reflecting the absolute change from Baseline to each post-Baseline time point (Week 4, 8, 12, 16, 20, 24, 36, 48, 60, 72 and Follow-Up).

The following plot will be produced for D_{LCO} and D_{LCO} % Predicted:

- Mean D_{LCO} (or D_{LCO} % Predicted) Change from Baseline (\pm SD) vs. Visit Week (Week 4, Week 8, Week 12, etc.) with lines for each treatment group.

A linear mixed-effects model (PROC MIXED) will be used for the analysis. The model will include the change from baseline in D_{LCO} (or D_{LCO} % Predicted) (measured at any time in the study) as the dependent variable and will include patient as a random effect, fixed effect of time and time-varying effects for treatment group and treatment-by-time interaction to account for those patients who switched dosing regimens from 50 mg once daily to 100 mg twice daily in Part B. To account for correlated repeated measures within patients a spatial power matrix will be used. Longitudinal plots at selected timepoints displaying the model adjusted, least square means and 95% confidence intervals will be produced.

All D_{LCO} data will be presented in a listing.

This document is confidential.

Statistical Analysis PlanSponsor: Avalyn Pharma, Inc.; Protocol No.: AP01-002

9. Exploratory**9.1. Correlation between weekly home spirometry measurements and in-clinic spirometry**

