- Summary statistics of CA19-9 and CA-125 reflecting the absolute change from Baseline to each post-Baseline time point (Week 4, 8, 12, 16, 20, 24, 36, 48, 60, 72 and Follow-Up).

The following plot will be produced for CA19-9 and CA-125:

- Mean CA19-9 (or CA-125) Change from Baseline (\pm SD) vs. Visit Week (Week 4, Week 8, Week 12, etc.) with lines for each treatment group.

Change from baseline in CA19-9 and CA-125 will be correlated with change from baseline in FVC at Weeks 4, 8, 12, 16, 20, 24, 36, 48, 60, and 72. Linear mixed-effects models (PROC MIXED) will be used for the analyses. The model will include the change from baseline in CA19-9 (or CA-125) (measured at Weeks 4, 8, 12, 16, 20, 24, 36, 48, 60, and 72) as the dependent variable and will include patient as a

This document is confidential.

Statistical Analysis PlanSponsor: Avalyn Pharma, Inc.; Protocol No.: AP01-002

random effect, fixed effects of time, change from baseline in FVC (measured at Weeks 4, 8, 12, 16, 20, 24, 36, 48, 60 and 72), baseline CA19-9 (or CA-125), visit and time-varying effects for treatment group and treatment-by-time interaction to account for those patients who switched dosing regimens from 50 mg once daily to 100 mg twice daily in Part B. To account for correlated repeated measures within patients a spatial power variance-covariance matrix will be used. Longitudinal plots at selected timepoints displaying the model adjusted, least square means and 95% confidence intervals will be produced.

A linear-mixed effects model (PROC MIXED) approach will be used to determine the repeated-measures correlation coefficient estimates for change from baseline in CA-19 (or CA-125) with change from baseline in FVC for each treatment group using change from baseline at Weeks 4, 8, 12, 16, 20, 24, 36, 48, 60 and 72. A normal approximation will be used to determine the estimate for the correlation coefficient (ρ_{hat}), the 95% confidence intervals for the correlation coefficient estimate and p-value. Spirometry data collected after patients switched dosing regimens from 50 mg once daily to 100 mg twice daily will be omitted from this analysis.

This document is confidential.

SAP Version: 3.0 (15JUL2021)
Controlled Document ID: **3903A.01**, Effective Date 29-Oct-2018
Filing requirements: TMF

Page 39 of 52

Statistical Analysis PlanSponsor: Avalyn Pharma, Inc.; Protocol No.: AP01-002

10. Safety

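### The all-study in-clinic FVC and DLCO models admit Follow-Up readings taken off AP01 and Part B readings on add-on nintedanib, with no rule or state for either

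*SAP*

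**What the plan says.** **Data entering the models.** SAP 8.1 defines the all-study FVC model with: "The model will include the change from baseline in in-clinic FVC (or FVC % Predicted) (measured at any time in the study"). SAP 8.2.6 defines the DLCO model with change "measured at any time in the study) as the dependent variable and will include patient as a random effect". The lung-function time points in SAP 8.1 are "Week 4, 8, 12, 16, 20, 24, 36, 48, 60, 72 and Follow-Up) as described in Section 6.1", so Follow-Up is one of them. SAP 8.2.6 has the same list.

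**What Follow-Up is.** Protocol 6.2.11: "Follow-up visits will occur 28 days after the End of Study visit for Part B". Spirometry and DLCO are among its procedures. Under the Protocol synopsis (Study Overview/Design), a patient either goes on to AP01-005 or stops dosing after Visit 12 and returns for Follow-up. The notes to Protocol Tables 5 and 6 say that patients enrolling in AP01-005 have no Follow-up visit. Under the synopsis (Study Duration), the study ends for non-rollover patients at their last Follow-up or Early Termination visit, so the Follow-Up reading lies within the study.

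**How treatment is modelled.** Both models use "time-varying effects for treatment group and treatment-by-time interaction to account for those patients who switched dosing regimens". The switch meant is the move from the lower to the higher dose; no other change of treatment is named.

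**Nintedanib.** Protocol 5.6: "During Part B of the study, the investigator may choose to add nintedanib, but not oral pirfenidone, to the patient's treatment regimen". Protocol 5.3 and 8.9.1 agree. Permitted use breaches no restriction, so the per-protocol exclusion for concomitant medicine in SAP 5.3 does not reach it.

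**Where the SAP does restrict data.** For the slope model in SAP 8.1: "Spirometry data collected after patients switched dosing regimen from 50 mg once daily to 100 mg twice daily will be omitted for this analysis". The CA19-9/CA-125 model in SAP 9.4 uses change "measured at Weeks 4, 8, 12, 16, 20, 24, 36, 48, 60, and 72) as the dependent variable", which leaves Follow-Up out.

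**The concern.** The stated objective (Protocol 2, SAP 3.2) is to estimate the effect of AP01 at each regimen. A treatment factor whose only levels are regimens has no place for a patient who stopped AP01 four weeks earlier, nor for one taking AP01 with a second antifibrotic. The SAP neither excludes nor flags such readings, and it does not say that it intends a treatment-policy estimate that would keep them on purpose.

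The adjusted means late in Part B are at stake. If lung function falls after AP01 is stopped, Follow-Up readings pull the fitted curve down, and only through patients who did not roll over. If nintedanib slows decline, readings on it pull the curve up. Early Termination readings taken after the last dose raise the same question, since SAP 6.4 maps them to a visit or date without reference to dosing.

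**Working it through.** **The plan's own precision figure.** SD 4.5 and n = 50 per group (SAP 3.5): 1.96 × 4.5/√50 = 1.247, which matches the stated 1.25. It refers to a simple group mean; the plan gives no precision figure for the all-study models.

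**Assumed antifibrotic effect.** SAP 3.5 gives Week 26 changes of -1.5 (oral pirfenidone) and -3.9 (placebo). Rate: (3.9 - 1.5)/26 = 0.0923 points per week. The documents give no figure for nintedanib or for loss of effect after stopping AP01, so this rate stands in for both.

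**Model used for sizing.** A straight line in time, fitted by least squares with every visit present. SAP 8.1 calls time continuous in the random part of the FVC model; linearity of the fixed part is my assumption. The result reported is the adjusted mean at a time point, so I use the fitted Week 72 value.

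*Follow-Up*
1. Visits are Weeks 4, 8, 12, 16, 20, 24, 36, 48, 60, 72 and 76. Mean 34.18; sum of squares about the mean 6763.6.
2. Weight of the Week 76 reading in the fitted Week 72 value: 1/11 + (72 - 34.18)(76 - 34.18)/6763.6 = 0.091 + 0.234 = 0.325. Its weight at Week 24 is 0.03.
3. Four weeks without AP01: 4 × 0.0923 = 0.37 points. Shift at Week 72: 0.325 × 0.37 = 0.12 points per attending patient.
4. If 25-50% of a group attend (assumed), the group value moves by 0.03-0.06. Over a wider assumed range, an off-drug fall of 0.5-2 points in 25-100% of a group, it moves by 0.04-0.65.

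*Nintedanib*
1. Visits are Weeks 4-72. Mean 30; sum of squares 4840.
2. Weight of week t in the fitted Week 72 value: 1/10 + (72 - 30)(t - 30)/4840. This gives 0.256 at Week 48, 0.360 at Week 60 and 0.464 at Week 72.
3. With a start at Week 36, those visits carry 12, 24 and 36 weeks of benefit: 0.256 × 12 + 0.360 × 24 + 0.464 × 36 = 28.4 weeks.
4. Shift for a share f of the group: f × 0.0923 × 28.4, which is 0.26 for f = 10% and 0.79 for f = 30%. Half the effect gives 0.13-0.39.
5. The raw shift in the Week 72 mean would be f × 0.0923 × 36 = 0.33-1.00. The linear fit spreads it, so the modelled figure is about 21% lower.
6. Wider assumed ranges, with a slowing of 0.5-2.4 points per 26 weeks in 10-40% of a group: 0.08-1.60 for a start at Week 24 and 0.03-0.57 for a start at Week 48.

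No comparable sizing is possible for DLCO, because the documents give no effect or SD for it.

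**The case against.** **Other Week 72 estimates exist.** A reader might infer that these models are the only long-term evidence. They are not. SAP 8.1 and 8.2.6 tabulate each visit separately, so the Week 72 summary holds no Follow-Up reading. SAP 6.1 splits Part B by switch history, and SAP 9.2 models home FVC to Week 72. This stands.

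**The coding is not stated.** A reader might infer that the SAP codes off-drug readings as being on the last regimen. It does not say so. What stands is narrower: a term with only regimen levels must either assign one of them or leave the reading undefined, and a rule is needed in both cases. Nor do the documents show that admitting these readings was an oversight. SAP 9.4 differs in wording but has no last-dose or nintedanib rule of its own.

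**Keeping every reading is legitimate.** A treatment-policy estimate is a sound choice for Early Termination and on-nintedanib readings, and dropping them risks losing the patients who declined. This also stands, and it is why the fix keeps them in the main model. It does not settle Follow-Up, which comes after planned completion of dosing and lies outside the 24 and 72 weeks named in the Protocol synopsis (Secondary Analyses).

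**Nintedanib uptake may be low.** The inclusion criteria select patients ineligible for oral pirfenidone and nintedanib under national formulary rules, or intolerant of or unwilling to start them. That argues against high uptake but does not exclude it. Crediting nintedanib added to AP01 with oral pirfenidone's full effect over placebo may also be generous.

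**Conclusion.** The gap is real but modest. Two kinds of reading enter the all-study in-clinic FVC and DLCO models without a rule: Follow-Up readings off AP01, from non-rollover patients only, and Part B readings on permitted nintedanib. On the assumptions shown, Follow-Up is a minor matter at group level. Nintedanib could be material at Week 72, at 0.26-0.79 points against a half-width of 1.25, but only if uptake reaches the assumed 10-30% from about Week 36. If time were fitted by visit category instead of linearly, Follow-Up would have much less influence on Week 72.

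Two stronger conclusions are not supported. A reader might infer that the primary result is biased; the Week 24 analysis covers Part A, where nintedanib is barred and Follow-Up does not occur, so it is not directly affected. A reader might also infer that nintedanib hides a true dose difference. The documents do not say which group would use more of it. Under protocol v2.1 the 50 mg patients convert to 100 mg twice daily in Part B, so only pre-switch Part B data could carry that contrast there. I am confident about the missing rule, and not about the size or direction of any bias.

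**What to change.** 1. In SAP 8.1 (all-study FVC model) and 8.2.6, replace the any-time clause with scheduled visits at Weeks 4-72, as SAP 9.4 already does. Label the Follow-Up summaries as off AP01.
2. Keep the Weeks 4-72 model with all readings, including Early Termination and on-nintedanib readings, as the main analysis, and say that it is a treatment-policy estimate.
3. Add one sensitivity run per endpoint that omits readings after the last AP01 dose and from the start of nintedanib onward.
4. Tabulate the number and timing of nintedanib starts by group. SAP 7.6 summarizes concomitant medication by class and lists it, but does not summarize timing.

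Cost: SAP wording, one small table and one extra run per endpoint. No new data are needed, because concomitant medications are already recorded on the eCRF. One Follow-Up reading per non-rollover completer leaves each model, as would any spirometry from the Day 588 safety visits in Protocol 6.2.10, which the SAP schedule does not list. The sensitivity run is itself open to informative censoring, since patients who stop AP01 or start nintedanib may be those declining. It should supplement the main model and not replace it.

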The DSMB for this study met on 12 OCT 2020 to review preliminary dose comparison data. It was determined that the 100 mg twice daily dose showed a trend for amelioration of FVC loss and recommended all patients in Part B be treated with the 100 mg twice daily dose. Therefore, all patients who participate in Part B after the implementation of this amendment will be treated with the 100 mg twice daily dose. Any patients already participating in Part B on the 50 mg once daily dose will be converted to the 100 mg twice daily dose regimen. Patients will have monthly telephone assessments and quarterly in-clinic assessments. All patients that complete the study visits through Part B will have the option to continue receiving AP01 by enrolling or planning to enroll in the AP01-005 study or to stop dosing after the EOS/Visit 12 and return for a Follow-up visit, 28 days after their End of Study visit.

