## 5.3. Study Restrictions

Patients are not to receive pirfenidone or nintedanib within 3 days prior to randomization to the study and during participation in Part A of the study. Nintedanib, but not oral pirfenidone, use is allowed if deemed necessary by the investigator during Part B of the study. In the event of an acute exacerbation, any treatment deemed necessary by the investigator is acceptable until the resolution of the event. Other than brief periods of medically appropriate treatment for acute IPF exacerbation, patients will not receive any other therapy for the treatment of IPF during Part A. If in the opinion of the investigator, a patient is in need of treatment with oral pirfenidone or nintedanib during Part A, the patient should be discontinued from the study and return to the clinic for their Early Termination visit. Oxygen use is allowed during the study.

Avalyn Pharma, Inc.  
AP01-002

Protocol v2.1  

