12 OCT2020

## 11 STATISTICS

### 11.1 Power and Sample Size Determination

This is an open-label study to determine safety and tolerability of AP01 50 mg once daily or 100 mg twice daily; both regimens being administered using the eFlow. With 50 patients per arm, we have a 92% chance of detecting an AE with a true population rate of 5%, as displayed in Table 10:

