**Table 10: Probability of observing adverse events**

	Actual probability of event		
	1%	5%	10%
Chance of observing $\geq 1$ event	0.395	0.923	0.995

The Phase 3 study of oral pirfenidone in patients with IPF (ASCEND) showed a standard deviation (SD) of 4.5 based on the imputed mean change in % of predicted FVC at Week 26. Assuming a SD of 4.5, with 50 patients per arm, a two-sided 95% CI for mean change from baseline in % of predicted FVC will extend 1.25 from the observed mean. The ASCEND study showed a decrease of 1.5 and 3.9 in % of predicted FVC at Week 26 in the pirfenidone and placebo arms, respectively. Table 11 shows results of the ASCEND active and placebo arms and potential observed differences in the AP01-002 study, assuming a similar SD.

Because we have no prior data on efficacy outcomes with our compound, we are unable to make well informed predictions of effect size or variability. In lieu of that information, we have included some estimates of confidence intervals based on prior oral pirfenidone studies; however, we cannot be confident that our product will behave similarly and would not base hypothesis tests on this information. This study will give us an idea of which endpoints are most likely to be positively impacted by our product as well as solid estimates of both effect size and variability. In addition, if the effect is due to AUC or multiple peaks/day in the ELF rather than peak levels, based on our modeling from the BAL cohort in the AP01-001 study, we have around 75% power to show a difference between arms. With this sample size we can be confident on selecting dosing regimen(s) for future trials.

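### The all-study FVC model (and the DLCO model) crosses current dose with time since baseline, so decline accrued on 50 mg is attributed to 100 mg after the switch and the long-term dose contrast is biased toward zero

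*SAP*

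**What the plan says.** The last model in SAP 8.1 takes change from baseline in in-clinic FVC or FVC % predicted, at any time in the study, as its outcome. Patient and continuous time are random effects. The fixed part is "fixed effect of time and time-varying effects for treatment group and treatment-by-time interaction to account for those patients who switched dosing regimens". The DLCO model in SAP 8.2.6 has "time-varying effects for treatment group and treatment-by-time interaction to account for those patients who switched dosing regimens", with a random patient effect and a spatial power matrix but no random slope. Neither model has a term for time since the switch, cumulative time on each dose, or level at the switch.

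The only time scale defined (SAP 6.2.5) counts days from the first dose in Part A. SAP 6.2.8 defines a dosing switch date.

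Switching is planned. The Protocol synopsis, Study Overview/Design, says: "Any patients already participating in Part B on the 50 mg once daily dose will be converted to the 100 mg twice daily dose regimen". Those entering Part B after the amendment go straight to 100 mg twice daily. SAP 6.1 also foresees patients who stay on 50 mg. No document gives the number switching or the weeks at which they switch.

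Other analyses treat the switch differently. The slope model for the primary endpoint (SAP 8.1), which is extended to Part B, and the home-spirometry model (SAP 9.2) both omit spirometry collected after the switch.

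**The concern.** The outcome is cumulative but the dose term is not. With a current-dose indicator and its product with time since first dose, the fitted mean for anyone now on 100 mg is the same line, whether they have had 100 mg since Day 1 or changed over last month. A switcher's lung function does not recover what was lost on 50 mg, so the observed values lie below that line and pull it down.

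This model yields adjusted means, intervals and longitudinal plots over the full study. Comparing the two regimens is a stated objective (Protocol 2, SAP 3.2), and 72-week results by arm are planned (Protocol synopsis, Secondary Analyses). At stake is a long-term dose contrast that is too small and a 100 mg curve that looks too poor. It would also sit beside a Part B slope analysis that handles the switch differently, with no rule for which of the two to rely on.

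**Working it through.** **The plan's own figures.** The SAP gives none for this model. Protocol 11.1 gives 50 patients per arm and an SD of 4.5. The stated confidence-interval half-width is reproduced: 1.96 × 4.5/√50 = 1.247 (1.25 stated). Protocol 11.1 also says "we have around 75% power to show a difference between arms" without stating the difference assumed. With a difference of 3.9 − 1.5 = 2.4, the standard error is 4.5 × √(2/50) = 0.90, 2.4/0.90 − 1.96 = 0.71, and power is 76%. That agrees with the stated figure, but the 2.4 is an assumption, because the plan attributes its figure to lavage-cohort modelling.

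**Assumed truth.** The Protocol says the oral pirfenidone trial "study showed a decrease of 1.5 and 3.9 in % of predicted FVC at Week 26 in the pirfenidone and placebo arms". For illustration, 50 mg declines by 3.9 points and 100 mg by 1.5 points per 24 weeks, and a switcher continues from the level reached. The true slope difference is 2.40 per 24 weeks. At Week 72 the true 100 mg mean is −1.5 × 3 = −4.5 and the true difference is 2.4 × 3 = 7.2.

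**Mechanism for one patient switching at week s, seen at week t > s.**
- True mean: −3.9·s/24 − 1.5·(t − s)/24
- Mean on the true 100 mg line: −1.5·t/24
- Gap: −2.4·s/24, which is −2.4 points for a switch at Week 24, −4.8 at Week 48 and −6.0 at Week 60

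The gap does not close with further follow-up. The model has no term for it.

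**Large-sample bias.** The coefficients of b0 + b1·t + b2·D(t) + b3·D(t)·t, with D = 1 on 100 mg, were computed as (ΣX′V⁻¹X)⁻¹ΣX′V⁻¹μ. Visits run from Week 4 to Week 72, with random intercept and slope and no dropout. Two variance set-ups were used:
- A: baseline error shared by every change (intercept SD = residual SD σ), σ from 1.5 to 3.0, slope SD = √(4.5² − 2σ²), so the Week 24 SD is 4.5.
- B: intercept, slope and residual SDs of 0, 4.03 and 2.0 (Week 24 SD 4.5) or 1.5, 4.0 and 2.5 (Week 24 SD 4.95).

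| Switching in the 50 mg arm | A: share of slope difference kept | B: slope difference (true 2.40) | A: share of Week 72 difference kept |
|---|---|---|---|
| All at Week 24 | 73-82% | 1.46-1.61 (33-39% lost) | 61-64% |
| Weeks 24-60, half to all switching | 31-67% | 0.65-0.84 (65-73% lost) | 28-51% |
| All at Week 48 | 31-55% | 0.69-0.74 (69-71% lost) | 28-35% |

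In the Weeks 24-60 row, set-up A loses 56-69% for σ up to 2.5. At σ = 3.0 it loses 33-47%. In set-up B the 100 mg mean at Week 72 is about −5.9 if all switch at Week 24 and about −6.8 with switches over Weeks 24-60, against −4.5. With no switchers the model is unbiased.

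**REML check.** Sixty simulated trials per row, 50 patients per arm; mean slope difference per 24 weeks (true 2.40):

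| Scenario | As written | Cumulative weeks per dose | Post-switch data omitted |
|---|---|---|---|
| All at Week 24, σ = 2 | 1.71 | 2.37 | 2.31 |
| Weeks 24-60, σ = 2 | 0.80 | 2.36 | 2.36 |
| Weeks 24-60, half stay on 50 mg, σ = 2 | 0.84 | 2.37 | 2.35 |
| Weeks 24-60, σ = 2.5 | 0.94 | 2.49 | 2.47 |

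**DLCO structure.** With a random intercept plus spatial power, the same FVC-scale truth and at least half switching, 48-100% of the slope difference and 27-74% of the Week 72 difference are kept. This is illustrative only: the documents give no DLCO decline rates.

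**The case against.** The strongest reply is that little depends on this model. The primary objective is safety. The primary efficacy endpoint is at Week 24, before Part B switching begins. Its slope model and Part B extension, and the home-spirometry model, drop post-switch data. The DSMB chose the regimen on preliminary 6-month data, before SAP 3.0 was dated. SAP 6.1 adds switcher and stayer groups and within-patient plots marking the switch, and SAP 7.1 summarises switch timing. All of this stands. A reader might infer that the study's main dose comparison is compromised; the documents do not support that.

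A reader might also infer that most of the dose effect is erased. That depends on switch timing, the fraction switching and the variance split. If all switch at Week 24, well over half of the slope difference remains.

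Two modelling points also stand. The sentence in SAP 8.1 says only that time is continuous, so time from first dose is the natural reading but an inferred one. And if response followed current dose at once, the model as written would be right and the cumulative-weeks model would overstate the difference. Against this, the SAP's own primary analysis treats the effect as one on slope.

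Two extensions are tempting and are not made here. The CA19-9 and CA-125 models (SAP 9.4) share the dose terms, but nothing in the documents says dose acts on a cumulative rate for these markers, and the model has further covariates. Nintedanib is permitted in Part B; whether to keep data after it starts is a separate estimand choice that has not been quantified.

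**Conclusion.** The point holds for the all-study in-clinic FVC model, and for DLCO if dose acts on its rate of decline. The stated terms attribute decline accrued on 50 mg to 100 mg. This biases the long-term dose contrast toward zero and makes the 100 mg adjusted means too low. Under −3.9 versus −1.5 points per 24 weeks, about 20-40% of the slope difference is lost if the whole 50 mg arm switches at Week 24. With staggered or late switching, which the conversion of patients already in Part B makes likely, the loss is usually more than half, about 55-70%, though smaller when residual error dominates.

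These sizes rest on the assumed declines, on time being counted from first dose, on an effect on rate rather than an immediate one, and on no dropout. This should be fixed before the final analysis, but it does not call the primary Week 24 result into question.

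**What to change.** In the all-study FVC model, and in the DLCO model, replace treatment and treatment-by-time with two fixed slopes: cumulative weeks on 50 mg and cumulative weeks on 100 mg at each visit. This is a linear spline with its knot at the dosing switch date of SAP 6.2.8. Alternatively, omit post-switch data, as the primary slope model in SAP 8.1 already does; this also removes the bias but discards follow-up. State that time is measured from first dose, and which dosing history each plotted adjusted mean represents. Keep the current-dose model as a sensitivity analysis only.

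The cost is a paragraph of SAP text and a few lines of PROC MIXED code; the switch date is already defined. The downside is that the replacement assumes no instantaneous effect of switching, and would overstate the dose difference if response followed current dose. Retaining the current-dose model as a sensitivity analysis lets a reader see how far the result depends on that assumption.
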